10.3 POPULATIONS FOR ANALYSES

10.3.1 Evaluable for Toxicity

All patients will be evaluable for toxicity from the time of their first treatment with olaparib.

10.3.2 Evaluable for Objective Response, Progression Free Survival and Soluble Mesothelin Levels and PFS

Only those patients who have measurable disease present at baseline, have received at least one cycle of therapy, have taken at least 50% of the doses per given cycle, and have had their disease re-evaluated will be considered evaluable for response. These patients will have their response classified according to the definitions stated below. (Note: Patients who exhibit objective disease progression prior to the end of cycle 1 will also be considered evaluable.)

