2 ELIGIBILITY ASSESSMENT AND ENROLLMENT

2.1 ELIGIBILITY CRITERIA

- 2.1.1 Inclusion Criteria
- 2.1.1.1 Patients must have histologically or cytologically malignant mesothelioma confirmed by the NCI Laboratory of Pathology. Patients with pleural, peritoneal, pericardial or tunica vaginalis mesothelioma are eligible.
- 2.1.1.2 Archival tumor samples must be available and sufficient for diagnostic and genetic testing; if archival sample insufficient for testing, subject must have lesions amenable to biopsy and be willing to undergo biopsy.
- 2.1.1.3 Patients must have measurable disease, as defined in sections 6.4.1 and 6.4.2.
- 2.1.1.4 Patients must have progressive disease at study entry
- 2.1.1.5 Patients must have received prior platinum and pemetrexed based therapies. Response to platinum is not an eligibility criterion for enrollment.
- 2.1.1.6 Age ≥18 years. Because no dosing or adverse event data are currently available on the use of olaparib in patients <18 years of age, children are excluded from this study, but may be eligible for future pediatric trials.
- 2.1.1.7 ECOG performance status ≤ 1 (see Appendix A).
- 2.1.1.8 Patients must have a life expectancy of ≥ 16 weeks
- 2.1.1.9 Patients must have adequate organ and marrow function ≤5days prior to C1D1 as defined below:

| leukocytes | ≥3,000/mcL |
|---------------------------|---|
| absolute neutrophil count | \geq 1,500/mcL without growth factor support |
| platelets | ≥100,000/mcL |
| hemoglobin | \geq 10 g/dL with no blood transfusion in the past 28 days |
| total bilirubin | ≤1.5 x ULN (unless Gilbert's Disease) |
| AST(SGOT)/ALT(SGPT) | \leq 2.5 X institutional upper limit of normal (\leq 5X ULN in the presence of liver metastases) |
| creatinine clearance | \geq 51 mL/min (calculated using the -Cockcroft-Gault formula . |

- 2.1.1.10 Pre-clinical data indicate that olaparib can have adverse effects on embryofetal survival and development. It is further not known whether olaparib or its metabolites are found in seminal fluid. For these reasons:
 - 2.1.1.10.1 **Women** of childbearing potential and their partners, who are sexually active, must agree to the use of 2 highly effective forms of contraception in combination (male condom plus one of the methods listed in section 2.1.1.10.3) or must totally/truly

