3.2 DRUG ADMINISTRATION

Olaparib at the dose of 300 mg will be given orally continuously twice daily, with doses taken at the same times each day approximately 12 hours apart. The correct number of 100mg or 150mg tablets comprising the appropriate dose should be taken at the same times each day with approximately 240 mL of water. Doses may be taken with a light meal/snack. The olaparib tablets should be swallowed whole and not chewed, crushed, dissolved, or divided.

Olaparib will be dispensed at the start of each 21-day cycle. Per the CCR policy for selfadministered oral investigational agents (PM-8) which will be followed in this protocol, patients will be provided with a pill diary (Appendix C), instructed in its use, and asked to bring it with them to each appointment.

Patients should be given clear instructions on how and when to take their study treatment. Patients will self-administer olaparib. Study site staff will make tablet counts at regular intervals during treatment. Compliance will be assessed by the tablet count and the information will be recorded in the appropriate section of the eCRF. All patients must return their bottle(s) of olaparib at the appropriate scheduled visit, when a new bottle will be dispensed. Patients will be instructed to notify study site personnel of missed doses. Dates of missed or held doses will be recorded by the patient on their patient diary and by the site staff on the eCRF.

If a patient misses more than 50% of the doses in any given cycle, the patient will be considered inevaluable for response per sections 10.3.2 and 10.3.3 and will be removed from the study.

Patients must return all containers and any remaining tablets at the end of the study.

If vomiting occurs shortly after the olaparib tablets are swallowed, the dose should only be replaced if all of the intact tablets can be seen and counted. Should any patient enrolled on the study miss a scheduled dose, the patient will be allowed to take the scheduled dose up to a maximum of 2 hours after that scheduled dose time. If greater than 2 hours after the scheduled dose time, the missed dose should not be taken, and the patient should take their allotted dose at the next scheduled time. Subjects should avoid grapefruit juice while on study, due to P450 interactions.

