3.5.3 Off-Study Criteria

- Completed study follow-up period
- Patient non-compliance
- Participant requests to be withdrawn from study (see section 3.5.4)

- Death
- Participant lost to follow-up
- The study is discontinued

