10.4 STATISTICAL ANALYSES

10.4.1 General Approach

Response rates will be determined in all patients and in the three comparison groups, based on all evaluable patients, and reported along with appropriate confidence intervals.

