15.3 APPENDIX C - PARTICIPANT OLAPARIB PILL DIARY

Today's date

Patient Name Patient Study ID

Cycle #

INSTRUCTIONS TO THE PATIENT:

- 1. Complete one form for each cycle (21 days).
- 2. You will take olaparib tablets twice a day ~12 hours apart on every day of the cycle. You must take the tablets with a large glass of water. A light snack (biscuits/ toast) is also recommended to help reduce nausea.
- 3. The olaparib tablets should be swallowed whole and not chewed, crushed, dissolved or divided.
- 4. You should avoid drinking grapefruit juice while on study.
- 5. If you miss a scheduled dose, you may take the scheduled dose up to 2 hours after the scheduled dose time. If it is more than 2 hours after the scheduled dose time, do not take the missed dose. You should then take the next dose at the scheduled time.
- 6. If you miss more than half of the doses (21 tablets) in any cycle, we will have to remove you from the study.
- 7. Record the date, the number of tablets you took, and when you took them.
- 8. If you have any comments or notice any side effects, please record them in the Comments column.
- 9. Please bring your pill bottle and this form to your physician when you go for your next appointment.

| DAY | DATE | # Tablets and When Taken | COMMENTS (side effects or missed doses) |
|-----|------|--------------------------|---|
| 1 | | AM PM | |
| 2 | | AM PM | |
| 3 | | AM PM | |
| 4 | | AM PM | |
| 5 | | AM PM | |
| 6 | | AM PM | |

| DAY | DATE | # Tablets and When Taken | COMMENTS (side effects or missed doses) |
|-----|------|--------------------------|---|
| 7 | | AM PM | |
| 8 | | AM PM | |
| 9 | | AM PM | |
| 10 | | AM PM | |
| 11 | | AM PM | |
| 12 | | AM PM | |
| 13 | | AM PM | |
| 14 | | AM PM | |
| 15 | | AM PM | |
| 16 | | AM PM | |
| 17 | | AM PM | |
| 18 | | AM PM | |
| 19 | | AM PM | |

| DAY | DATE | # Tablets and When Taken | COMMENTS (side effects or missed doses) |
|-----|------|--------------------------|---|
| 20 | | AM PM | |
| 21 | | AM PM | |

| Patient's Signature: | D | Date: | |
|----------------------|---|-------|--|
|----------------------|---|-------|--|

The Study Team will complete this section:

- 1. Date patient started protocol treatment
- _____ 2. Date patient was removed from study therapy _____
- 3. Total number of pills taken this cycle (Days 1-21)

Physician/Nurse Signature _____

15.4 APPENDIX D – ACTIONS REQUIRED IN CASES OF LIVER BIOCHEMISTRY AND EVALUATION OF HY'S LAW

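### The only planned ORR drops treated patients because of events after treatment starts; report an all-treated ORR beside it and keep documented responses

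*Combined protocol and SAP*

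**What the plan says.** The primary endpoint is the ORR overall and in three mutation groups (section 10.1.1). Section 6.4.5 defines the ORR without naming a denominator. Section 10.4.1 supplies one: response rates are to be "determined in all patients and in the three comparison groups, based on all evaluable patients". The closing words govern the sentence, so all patients there means the groups pooled, not everyone treated.

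Section 10.3.2 defines evaluable by four conditions: measurable disease at baseline, at least one cycle received, adherence and re-evaluation. The last two read "have taken at least 50% of the doses per given cycle, and have had their disease re-evaluated will be considered evaluable for response". One exception keeps patients with objective progression before the end of cycle 1. The first condition selects nobody further, because entry already demands it: "Patients must have measurable disease, as defined in sections 6.4.1 and 6.4.2" (section 2.1.1.3).

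Section 3.2 shows how far the adherence condition reaches: "If a patient misses more than 50% of the doses in any given cycle, the patient will be considered inevaluable for response". Section 10.2 budgets for it cycle by cycle.

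Only toxicity has an all-treated set (section 10.3.1). Sections 10.4.7 and 10.4.9 plan no subgroup or exploratory analyses, so no all-treated ORR appears elsewhere.

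**The concern.** A response rate computed in patients selected by what happened after the first dose is not the response rate of the patients who were treated. Two routes out of the denominator pull in opposite directions.

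- **Upward.** A treated patient who dies, or stops early for toxicity or clinical decline, without objective progression and without a re-scan is not counted. Such patients are unlikely to be responders.
- **Downward.** A patient with a documented response who later misses more than half the doses of a single cycle becomes inevaluable. Nothing in the plan keeps that response. The best-overall-response rules in sections 6.4.1.3.3 and 6.4.2.2 classify a response, but do not restore a patient whom section 3.2 has excluded. Longer treatment means more cycles in which this can happen.

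The ORR is read against a rate of about 20%, and the results are to inform whether more patients are enrolled by amendment (sections 10.2 and 10.4.2). A systematic shift is not reflected in the confidence interval, and no table of exclusions is planned.

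**Working it through.** **Inputs.** Section 10.2 gives 30 evaluable patients, a ceiling of 40, non-compliance of 10% per cycle, an average of 3 cycles, and a rate of interest near 20%. The responder counts below are assumptions, since the documents give none.

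1. **The plan's own figures.**
   - *Precision.* The exact (Clopper-Pearson) 90% interval for 15/30 is 33.9% to 66.1%, a half-width of 16.1 points, which matches the stated 16. For 6/30 it is 9.1% to 35.7%, or −10.9/+15.7 points, close to the stated 10 to 15.
   - *Ceiling.* Compounding the loss gives 30/0.9³ = 30/0.729 = 41.2. Adding it gives 30 × 1.3 = 39. Both are near 40. A single 10% loss would need only 30/0.9 = 33.3, so 34. The ceiling therefore fits a rule that applies in every cycle.

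2. **Expected loss to non-compliance.** 1 − 0.9³ = 27.1%. Of 40 treated, 40 × 0.729 = 29.2 would stay evaluable.

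3. **Upward route.** Start from 6/30 = 20.0% in the evaluable set and add m treated non-responders who were never re-scanned: 6/(30 + m).
   - m = 1: 6/31 = 19.4%
   - m = 3: 6/33 = 18.2%

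4. **Downward route.** Remove one documented responder from 6/30: 5/29 = 17.2%. As an average effect at 10% per cycle, if responders stay on treatment g cycles longer than non-responders, a true 20% reads as 0.2 × 0.9^g / (0.2 × 0.9^g + 0.8).
   - g = 0: 20.0%
   - g = 1: 0.18/0.98 = 18.4%

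5. **At the ceiling.** With 40 treated, 30 evaluable, 6 responses among the evaluable and r among the 10 excluded, the all-treated ORR is (6 + r)/40. The evaluable-set result is 6/30 = 20.0% (95% CI 7.7% to 38.6%).

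| r (assumed) | All-treated ORR | 95% CI |
|---|---|---|
| 0 | 6/40 = 15.0% | 5.7% to 29.8% |
| 2 | 8/40 = 20.0% | 9.1% to 35.6% |
| 3 | 9/40 = 22.5% | 10.8% to 38.5% |

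The sign of the difference depends on r: below 2 the evaluable ORR is the higher figure, above 2 the lower.

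**The case against.** **The never-re-scanned route is narrow.** This largely stands. Section 10.3.2 keeps early objective progressors. The study calendar schedules imaging at the discontinuation visit for patients who stop for a reason other than progression (section 3.4, footnote 14). Follow-up scans then continue until progression (footnote 15, section 3.5.2). What remains are patients who die or are lost before a scan, and those who stop before receiving a full cycle without objective progression.

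**The evaluable set is an open design choice.** The 30 patients, the precision and the ceiling are all set on evaluable patients, in a self-described pilot with no formal test. A reader might infer that the all-treated ORR should become the main result. The documents do not support that as a correction: it would change the quantity on which the sizing rests. A second line beside the first does not.

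**Readers could work it out.** In part. All treated patients are in the toxicity set, so responders over treated could be calculated. Responders who had been struck out, and the reasons for exclusion, would stay hidden.

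Three stronger inferences also fail:

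- *That the true figure is 15.0% when the plan reports 20.0%.* The allowance up to 40 patients is for dosing non-compliance, and nothing says that those patients do not respond.
- *That one exclusion turns 2/20 into 1/20 and stops accrual.* This needs a noted response to be withdrawn and the patient replaced, which no section describes.
- *That the diary shifts the analysis threshold.* It says "If you miss more than half of the doses (21 tablets) in any cycle, we will have to remove you from the study". A cycle has 21 × 2 = 42 doses, so 21 is half the doses. At 300 mg from 150 mg or 100 mg tablets, a cycle is 84 or 126 tablets. This is most likely a slip between doses and tablets, and the diary does not define the evaluable set.

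**Conclusion.** The point holds in a limited form. The only planned primary ORR rests on a set defined, beyond an entry criterion, by exposure, per-cycle adherence and re-evaluation after treatment starts. No all-treated ORR is planned, and no rule keeps a documented response.

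The net direction and size cannot be determined from the documents. Under the assumed counts, a few patients move the estimate by roughly 1 to 3 points. At the accrual ceiling, with none to three responders among ten excluded, the all-treated ORR lies between 15.0% and 22.5%; the lower end is an extreme, not an expectation. All these shifts lie within the planned precision of about ±10 to 15 points. The reason to act is that sampling error and systematic exclusion are different things, and only the first is reported.

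**What to change.** In sections 10.3.2 and 10.4.1:

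- Keep the evaluable-set ORR. Beside it, overall and by comparison group, report the ORR in all treated patients with measurable disease at baseline, counting those without a post-baseline assessment as non-responders.
- State that a documented response counts toward the ORR whatever the later adherence.
- Tabulate each exclusion with its reason and best response.

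The cost is one more ORR line and one table, with no extra patients or visits. The all-treated ORR may look less favourable.

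Minor points to settle in the same amendment, which do not carry the conclusion:

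- Say in section 10.4.6 which 20 patients the 0-1 rule counts.
- Reconcile section 3.2, where such a patient is inevaluable "and will be removed from the study", and "Patient non-compliance" as an off-study criterion (section 3.5.3), with sections 3.5.1 and 3.5.2. Section 3.5.1 also lists non-compliance as a reason to stop therapy only, and section 3.5.2 treats stopping therapy as distinct from leaving the study.
- Reconcile whether held doses count toward the 50%. Section 3.2 names them separately ("Dates of missed or held doses will be recorded by the patient on their patient diary") and section 10.2 speaks of non-compliance, which suggests they do not. But section 10.3.2 counts doses taken, and a 4-week hold under section 3.3 can span a 21-day cycle.
- Reconcile the tablet count in Appendix C with the 50%-of-doses rule.

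No clinical rule is proposed.

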10.3.3 Evaluable Non-Target Disease Response

Patients who have lesions present at baseline that are evaluable but do not meet the definitions of measurable disease, have received at least one cycle of therapy, have taken at least 50% of the doses per given cycle, and have had their disease re-evaluated will be considered evaluable for non-target disease. The response assessment is based on the presence, absence, or unequivocal progression of the lesions.

10.4 STATISTICAL ANALYSES

10.4.1 General Approach

Response rates will be determined in all patients and in the three comparison groups, based on all evaluable patients, and reported along with appropriate confidence intervals.

10.4.2 Analysis of the Primary Endpoints

After enrollment, when the mutation determination is possible, the response rates will be assessed according to each of the three categories of mutation and the results reported accordingly. The proportions responding in each category will be presented along with 95% confidence intervals. The results obtained will be used to determine if there are any further patients to be enrolled following an amendment taking into consideration the preliminary results obtained.

10.4.3 Analysis of the Secondary Endpoint(s)

The secondary objectives will be assessed using the following measures.

Descriptive tabulations of toxicity will be provided.

Kaplan-Meier analysis of PFS will be performed, including reporting PFS at relevant time points, along with 95% confidence intervals.

Responders vs. non-responders will be compared with respect to serum mesothelin and MPF baseline levels or changes over time (see section 5.1 for biomarkers to be reported), with results compared between response categories using two-tailed Wilcoxon rank sum tests.

Serum mesothelin and MPF at baseline will be categorized into two groups of approximately equal size and tested for their association with PFS using Kaplan-Meier curves and two-tailed log-rank tests. Changes in serum mesothelin and MPF will be determined up until the end of treatment, and landmark analyses will be used to assess their association with PFS.

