1 INTRODUCTION

1.1 STUDY OBJECTIVES

1.1.1 Primary Objective

- Determine the efficacy with respect to objective response rate of olaparib in patients with malignant mesothelioma based on somatic or germline mutation status of DNA repair genes
- 1.1.2 Secondary Objectives
 - To assess the safety and tolerability of olaparib in patients with mesothelioma
 - To assess progression free survival in patients with mesothelioma treated with olaparib monotherapy
 - To investigate the potential of soluble mesothelin levels and levels of megakaryocyte potentiating factor to predict any therapeutic response

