10.2 SAMPLE SIZE DETERMINATION

The primary objective of this pilot study is to obtain preliminary estimates of the overall response rates to olaparib in patients with malignant mesothelioma according to their individual comparison group:

- Comparison Group 1 Patients with a germline mutation in DNA repair genes (estimated at 10-12% of all patients)
- Comparison Group 2 Patients with *BAP1* somatic mutations (estimated at 50-60% of all patients)
- Comparison Group 3 Patients with neither germline DNA repair mutations nor BAP1 somatic mutations (estimated at 30-40% of all patients).

All patients will be enrolled without consideration of their mutation status, and then the results will be retrospectively categorized and evaluated by mutation type. These results will be used to determine if there are any further patients to be enrolled following an amendment taking into consideration the preliminary results obtained.

It would be desirable if overall there was at least approximately a 20% response rate. The study will initially plan to enroll 30 evaluable patients in order to estimate the overall response rate with a maximum two-sided 90% confidence interval width of +/- 16%. If the observed response rate were 15-20%, the confidence interval width overall would be approximately +/-10-15%. Thus, 30 patients are adequate for an overall assessment of response. If during the initial 20 patients evaluated, there are 0-1 responses noted, then no further patients will be enrolled as soon as this can be determined since the upper one-sided 90% confidence interval bound on 1/20 is 18.1%, which is below the approximate response rate of interest. Because accrual is proceeding rapidly on the study and continued enrollment is desirable at this time, up to 25 total patients may be enrolled (5 additional patients) while awaiting the response evaluations among the first 20 patients.

It is expected that 30 evaluable patients can be enrolled in approximately 12-18 months. As patient non-compliance with study drug dosing will prevent them from being evaluable, the accrual ceiling must be adjusted accordingly. Estimating an average of 3 cycles of study therapy and a non-compliance rate of 10% per cycle the accrual ceiling will be set at 40 patients.

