10.4.6 Planned Interim Analyses

If during the initial 20 patients evaluated, there are 0-1 responses noted, then no further patients will be enrolled as soon as this can be determined. since the upper one-sided 90% confidence interval bound on 1/20 is 18.1%, which is below the approximate response rate of interest. Because accrual is proceeding rapidly on the study and continued enrollment is desirable at this time, up to 25 total patients may be enrolled (5 additional patients) while awaiting the response evaluations among the first 20 patients.

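### Section 10.4.3 relates mesothelin and MPF to response only by a responder/non-responder Wilcoxon test, which is uninformative with 0 or 1 responders and weak with 3 to 6; a correlation with percentage tumour change should be added.

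*Combined protocol and SAP*

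**What the plan says.** The secondary objective in section 1.1.2 is "To investigate the potential of soluble mesothelin levels and levels of megakaryocyte potentiating factor to predict any therapeutic response". Section 10.1.2 lists three endpoints under it: a comparison of responders with non-responders, a preliminary evaluation against objective response, and a preliminary evaluation against PFS.

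For response, section 10.4.3 states: "Responders vs. non-responders will be compared with respect to serum mesothelin and MPF baseline levels or changes over time", "with results compared between response categories using two-tailed Wilcoxon rank sum tests". No other method for response is given. For PFS, the same section divides each baseline marker into two groups of similar size for log-rank tests and uses landmark analyses for marker changes. Section 10.4.9 plans no exploratory analyses. No significance level or power is stated for any marker test.

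On numbers, section 10.2 says "The study will initially plan to enroll 30 evaluable patients" and "the accrual ceiling will be set at 40 patients". Its target is "It would be desirable if overall there was at least approximately a 20% response rate", and it also considers an observed rate of 15–20%. Section 10.4.6 says "If during the initial 20 patients evaluated, there are 0-1 responses noted, then no further patients will be enrolled", and lets enrolment run to 25 while the first 20 are being read.

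On data, markers are drawn before dosing on Day 1 of every 21-day cycle and at end of treatment (5.1.2), and scans are taken every 6 weeks (3.4, 6.4). A sum of target-lesion diameters (6.4.1.1) or a total tumour measurement for pleural disease (6.4.2.1) is recorded, and partial response is a cut at a 30% decrease in that measure.

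**The concern.** The trial records tumour size on a continuous scale, but the marker–response analysis uses only whether a patient crossed the response threshold. At the response rates the plan considers, that sets a handful of responders against everyone else. The plan also has a stopping rule that acts when very few responses are seen, and in that situation the only response analysis named for the markers may be impossible to compute or unable to show anything. At stake is a secondary objective: a real marker–response relation could be missed although the data to estimate it are in hand. The primary response-rate analysis is not affected.

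**Working it through.** **The plan's own figure.** The upper one-sided 90% exact bound on 1/20 is the p that solves P(X ≤ 1 | 20, p) = 0.10. At p = 0.181: 0.819^20 + 20 × 0.181 × 0.819^19 = 0.018 + 0.081 = 0.0999. The stated 18.1% is reproduced.

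**Smallest attainable p.** With r responders among n patients, the most extreme ranking is one of C(n, r), so the smallest exact two-sided Wilcoxon p is 2/C(n, r).
- r = 0: no test exists.
- r = 1: 2/20 = 0.10; 2/25 = 0.08; 2/30 = 0.067; 2/40 = 0.05. It never falls below 0.05 up to the accrual ceiling. The normal approximation gives 0.091–0.119 over the same range of n.
- r = 2: 2/190 = 0.0105 (n = 20); 2/300 = 0.0067 (n = 25).

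**Chance of 0 or 1 responders in total.** P = (1−p)^n + n·p·(1−p)^(n−1). For example, at n = 20 and p = 0.10: 0.122 + 0.270 = 0.392. The n = 20 column is also the probability of stopping. The last column is 1 minus the n = 25 figure divided by the n = 20 figure; at p = 0.10, 1 − 0.271/0.392 = 0.31.

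| True ORR | 20 evaluable | 25 evaluable | P(2 or more of 25, given a stop) |
|---|---|---|---|
| 20% | 7% | 3% | 60% |
| 15% | 18% | 9% | 47% |
| 10% | 39% | 27% | 31% |
| 5% | 74% | 64% | 13% |

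**Information lost by the yes/no split.** If marker and tumour change are bivariate normal, splitting tumour change at fraction q keeps φ(z_q)²/[q(1−q)] of the information.
- q = 0.20: 0.280²/0.16 = 0.490, a loss of 51%.
- q = 0.15: 0.426, a loss of 57%.
- q = 0.10: 0.1755²/0.09 = 0.342, a loss of 66%.

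Thirty patients then count as about 30 × 0.490 ≈ 15, or 30 × 0.342 ≈ 10.

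**Power.** Simulated with 30 complete pairs, bivariate normal, two-sided 0.05. Three to six responders is 10–20% of 30. Correlation and alpha are assumptions.

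| Correlation | Wilcoxon, 3–6 responders | Spearman |
|---|---|---|
| 0.3 | 12–16% | 34% |
| 0.5 | 26–45% | 77% |
| 0.6 | 41–63% | 93% |

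These carry simulation error. A separate set of 2,000 runs per cell gave 11–18%, 29–42% and 41–62% for Wilcoxon, and 32–36%, 75–78% and 92–93% for Spearman. Reaching two responders helps little: at n = 20 and correlation 0.5, power is 17% for Wilcoxon and 57% for Spearman.

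**Missing later samples.** Day 1 of cycle 3 (C3D1) falls at the first 6-week scan. A patient who progresses on that scan leaves therapy (3.5.1) and may have no C3D1 draw. The next sample comes about 30 days after the last dose and is not required if the patient cannot return (3.4, footnote 2). If the worst 20%, 30% or 40% of tumour changes are lost in this way (assumed fractions; correlation 0.5, 30 patients before loss), Spearman power for marker change falls to about 47%, 37% and 27%, against 32%, 24% and 19% for Wilcoxon with 6 responders. The baseline-marker correlation does not need that sample.

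**The case against.** Four points can be made for the plan.

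1. A reader might infer that a futility stop always leaves 0 or 1 responders. It does not. The rule counts the first 20 evaluated, and up to 25 may be enrolled by then; if all 25 are evaluable, 13–60% of stopped trials would have two or more responders at true rates of 5–20%, and p < 0.05 is then attainable. This stands, so the limitation has to be tied to the total number of responders and not to the stop.

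2. A reader might infer that this outcome is likely, or that the marker objective would then be unanswerable. At the 15–20% rates in section 10.2, the chance of 0–1 responders is 7–18% with 20 evaluable patients and 3–9% with 25. It is large only at lower rates, which the documents do not put forward. The PFS analyses in 10.4.3 need no responders, so the markers' link to outcome does not rest on this test alone. They address a different endpoint, however; sections 1.1.2 and 10.1.2 name response in its own right.

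3. The gain from a correlation is not assured. At correlation 0.3 its power is only about a third, and for marker change, selective loss of early progressors removes much of the advantage. This stands, and it argues for relying on the baseline marker.

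4. A reader might infer that the correlation should replace the responder comparison. Section 10.1.2 defines the endpoint through objective response, which is confirmed and takes account of new and non-target lesions. Percentage change at one scan does neither, and it mixes two measuring rules. Replacement would be a preference; only an addition is supported. The work is also preliminary, with no stated alpha, so p < 0.05 is a conventional yardstick and not the plan's own.

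**Conclusion.** The point holds as a cheap improvement to a secondary analysis, not as an error in the primary one. The responder/non-responder Wilcoxon test is the only specified route from the markers to response. With 0 or 1 responders in total it cannot yield p < 0.05 at any size up to 40 patients; this is exact and needs no model. Whether that happens depends on the true response rate and on how many of the 20 to 25 patients are evaluable. With 3–6 responders among 30, the split discards about 51–66% of the information and power falls well below that of a correlation. Those sizes assume bivariate normality, complete pairs, correlations of 0.3–0.6 and a two-sided 0.05 level, none of which the documents give.

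**What to change.** In section 10.4.3, keep the responder/non-responder comparison and add:

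- A prespecified Spearman correlation, with confidence interval, of baseline mesothelin and of baseline MPF with percentage change in tumour measurement at the first 6-week scan. Best percentage change is supportive.
- Results for pleural (modified RECIST) and non-pleural disease separately as well as pooled, or ranks formed within each measuring rule. Section 10.4.7 says no subgroup analyses will be done, so separate reporting needs a line there.
- The correlation for marker change from C1D1 to C3D1 as supportive only, with the number of missing C3D1 samples reported.
- A rule for pairing marker draws with scans, since scans have a 7-day window and cycles may be delayed by up to two weeks (3.4).
- A statement that the Wilcoxon test will not be run with no responders and will be descriptive with one.

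This needs no new samples, scans or patients. The costs are one extra analysis, and a tumour measure that misses progression by new lesions alone and drops patients with no follow-up measurement. It should be written in before marker results are seen, so that it is not a rescue after few responses.
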